6.7 Sensitivity analyses

The following sensitivity analyses will be performed for the primary analysis:

- According to the four definitions of the primary outcome of COVID-19 infection (ie. positive test only, symptoms only, clinical diagnosis only, hospitalized only)
- Imputing unexplained drop-outs as events. Healthcare workers that are lost to follow-up will be treated as positive for COVID-19 infection.

In the event that the estimated hazard ratio of treated versus control in the primary analysis is 0.8 or less, but no statistical significance can be established due to a small sample size, an alternative approach such as empirical Bayesian meta-analysis will be employed to leverage published local data.

7 Minimization of study bias

As this is an observational study based on self-reported information from HCWs, there are several potential limitations and biases that will need to be considered, as follows:

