8.7.6 Sensitivity Analyses

Among the sensitivity analyses, the adjusted analyses of the primary outcome will be replicated:

- According to the subgroup of HCWs for which PCR-confirmed absence of infection at index date is demonstrated.
- According to the subgroup of HCWs for which serology results are available at entry and follow-up.
- Using the infection status and timing as self-reported only.
- Imputing unexplained drop-outs as events.
- According to the time from index date to entry in the registry date.

As part of a risk mitigation plan and for further insights generation, e.g., in the case of low number of events or unexpectedly low exposure to potential prophylactic treatments, alternative approaches will be considered to maximize the power and enhance the robustness of the proposed study. In this case, additional information e.g., from published local data could be leveraged using Bayesian modelling approach on the incidence dynamics modelling and association analyses, together with impact assessments.

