8.7.7 Determination of Sample Size

The targeted sample size of approximately 10,000 HCWs assumes that 20% of the study population are non-exposed to potential prophylactic treatments, with a baseline risk of SARS-CoV-2 infection in the study period of 10% (for unexposed: not treated with potential prophylactic treatment). A total of N=10,000 allows for 80% power to identify an effect size of Relative Risk = 0.78.

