5 Determination of Sample Size

The targeted sample size of approximately 10,000 HCWs assumes that 20% of the study population are non-exposed to potential prophylactic treatments, with a baseline risk of SARS-CoV-2 infection in the study period of 10% (for unexposed: not treated with potential prophylactic treatment). A total of N=10,000 allows for 80% power to identify an effect size of Relative Risk = 0.78.

If these sample sizes are not reached with respect the study population being exposed/non-exposed to potential prophylactic treatments, the relative risk may be detected with lower power or it may not be statistically significant. However, the secondary objectives can still be examined.

6 Statistical analysis

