6.1 Overview

All statistical analyses will be conducted using R (version 1.3.1093), unless otherwise specified.

For all descriptive analyses, categorical variables will be summarized by number of observations and percentage (%). Percentages will be rounded to one decimal place and will be based on available observations (known values), unless otherwise specified. Continuous variables will be summarized using descriptive statistics (n, mean, with standard deviation; minimum, first quartile, median, third quartile,

and maximum). Outliers will be included in descriptions as part of presenting ranges and percentiles (25th and 75th). The mean and SD will be rounded to one decimal place.

All statistical tests will be two-sided and at 5% level of significance.

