6.2.2 Missing values for outcomes

Specific imputation methods will not be used for outcome variables. However, for descriptive analyses, each variable will be described with frequencies of missing and “Not Known” values, where applicable.

Other methods, including complete case analysis, will be considered when appropriate. For ‘time-to-event’ outcomes, patients who are lost to follow-up prior to the time point of interest will be censored.

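### Between censoring lost HCWs and counting them as infected in both groups, the SAP specifies no drop-out analysis, and the second rule does not bound the treatment contrast

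*SAP*

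**What the plan says.** SAP 6.2.2 uses no specific imputation for outcomes. For time-to-event outcomes, "patients who are lost to follow-up prior to the time point of interest will be censored". It adds that other methods, including complete-case analysis, may be considered, but specifies none.

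The drop-out bullet in SAP 6.7 opens with the same words as protocol 8.7.6, "Imputing unexplained drop-outs as events", and then explains them: "Healthcare workers that are lost to follow-up will be treated as positive for COVID-19 infection". The first phrase covers a subset of losses and the second covers all of them. Neither document defines an unexplained drop-out, gives an expected drop-out rate, or dates the imputed event, which a Cox model needs.

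Protocol 8.9 recognises that loss may differ by COVID-19 status. It relies on secondary contacts, who it says address the bias at least in part, and on a description of losses by risk profile and prophylaxis use. Protocol 8.7.4 leaves the handling of unexplained drop-outs to discussion with the Scientific Advisory Committee, and the SAP records no result of that discussion.

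**The concern.** Censoring is unbiased only if, given the model covariates, lost HCWs have the same infection hazard as those who stay. The protocol doubts this, so the check has to show how wrong the assumption could be before the conclusion changes.

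Counting every lost HCW as a case is extreme for absolute risk but not for the comparison of groups. It adds non-cases to both groups at the rate of drop-out. A harmless, equal loss can then make a real effect seem to vanish, and a modest difference in loss can reverse an effect or create one. A reader of the report could not tell which had happened.

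The two terms in the 6.7 bullet add a second problem. Protocol Appendix 2 collects infected/uninfected status from the secondary contact. Read literally, the second sentence could count as infected an HCW whose contact reported no infection.

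**Working it through.** **Inputs.** SAP section 5 and protocol 8.7.7: N = 10,000; the plan "assumes that 20% of the study population are non-exposed to potential prophylactic treatments", so 2,000 controls and 8,000 treated; control risk 10%; RR 0.78, so treated risk 0.78 × 10% = 7.8%. SAP 6.1: "All statistical tests will be two-sided and at 5% level of significance". The loss rates below are assumptions.

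**The plan's own figure.** SAP section 5: "A total of N=10,000 allows for 80% power to identify an effect size of Relative Risk = 0.78". Expected infections are 2,000 × 0.10 + 8,000 × 0.078 = 824 (8.24%). The Schoenfeld formula with 824 events, ratio 0.78 and a 20:80 split gives z = √(824 × 0.2 × 0.8) × |ln 0.78| − 1.96 = 11.48 × 0.2485 − 1.96 = 0.89, a power of 81.4%. This agrees with the stated 80%. A plain two-proportion comparison gives 87.7%.

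**Effect of the 6.7 rule.** With true risk p and loss L unrelated to infection, the counted risk is p + L(1 − p). The share of counted events that are uninfected drop-outs is L(1 − 0.0824) / [0.0824 + L(1 − 0.0824)].

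| Assumed loss, both groups | Control | Treated | RR (true 0.78) | Share from drop-out |
|---|---|---|---|---|
| 10% | 0.1900 | 0.1702 | 0.90 | 52.7% |
| 20% | 0.2800 | 0.2624 | 0.94 | 69.0% |
| 30% | 0.3700 | 0.3546 | 0.96 | 77.0% |

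Unequal loss:

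- 25% treated, 20% control: a true 0.78 gives 0.3085 / 0.2800 = 1.10; a true 1.00 gives 0.3250 / 0.2800 = 1.16.
- 20% treated, 25% control: a true 0.78 gives 0.2624 / 0.3250 = 0.81; a true 1.00 gives 0.2800 / 0.3250 = 0.86.

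**When drop-outs become the majority.** The share reaches 50% at L = 0.0824 / 0.9176 = 9.0%. With constant competing hazards of infection and loss the crossover is about 8.3%, and if losses are all counted before infections it is 7.6%. If control risk were 20% (treated 15.6%, overall 0.2 × 20% + 0.8 × 15.6% = 16.5%), the crossover rises to 0.1648 / 0.8352 = 19.7%, or about 16% with competing hazards.

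**Cross-check on the hazard scale.** The planning risks imply HR = ln(0.922) / ln(0.90) = 0.77. Adding equal drop-out hazards for 10%, 20% and 30% loss moves it to 0.89, 0.93 and 0.95. Power is then 53%, 35% and 25%, against 83%, 81% and 78% under plain censoring. With 25% treated and 20% control loss the HR is (0.0812 + 0.2877) / (0.1054 + 0.2231) = 1.12. The pattern is the same.

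**The case against.** The strongest reply is that drop-out is not left to these two rules. Secondary contacts recover the status of non-responders, and losses are to be described by prophylaxis use, which would reveal unequal loss. Facility-level counts of infections and deaths are compared with the survey data. The Cox model forces in facility and country and considers household, contact and PPE covariates, so censoring need only be independent given those retained. Also, with equal loss the rule attenuates, so a protective result that survives it is informative. All of this stands as mitigation, but none of it is a specified analysis that varies the assumption about lost HCWs. SAP 7.1 and 7.5 cite inverse probability weighting in a section 5.4.2 that the SAP does not contain, and for enrolment and indication bias. A paper on censoring weights is in the reference list, but no such analysis is described.

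A reader might infer three stronger points, which the documents do not support:

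- **That the SAP departs from the protocol by widening the imputed set.** The SAP bullet begins with the protocol's own phrase, so the conflict lies inside one bullet.
- **That most events in the check will be drop-outs.** This needs a drop-out rate, and none is given. The 10% control risk is a planning value. The composite in SAP 3.5.1 includes diagnosis by symptoms, and HCWs already infected at enrolment are eligible, so the event count could be higher.
- **That N = 10,000 already allows for 20% loss.** A two-proportion calculation needs 7,985, and 7,985 / 0.80 = 9,982, but neither document states an allowance, and the events formula reproduces 80% without one.

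**Conclusion.** The concern holds as a gap in the specified sensitivity analyses. Only censoring and lost-as-infected are specified for the primary outcome, and the second does not bound the treatment contrast. Under the planning risks the distortion is clear at 10% equal loss (0.78 to 0.90), and a five-point difference in loss around 20 to 25% is enough to reverse the sign of the check.

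The size rests on assumed loss rates, on loss unrelated to infection, and on cumulative risk ratios, whereas the planned measure is a hazard ratio. If infected HCWs are likelier to be lost, some imputed cases are real and the figures change. The reversal concerns the sensitivity result; it does not show that the primary estimate is wrong. The imputed set and event date are undefined whatever the drop-out rate.

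**What to change.** In SAP 6.7:

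1. Limit the imputed set to HCWs whose infection status is still unknown after secondary contact, and date the imputed event, for example at the first missed survey.
2. Add a tipping-point analysis that varies the infection risk of lost HCWs separately in treated and control and reports where the conclusion changes. For illustration, take 20% loss in each group, the planning risks in those retained, and lost controls at 10%. The RR reaches 1 when lost treated HCWs have a risk of (0.10 − 0.8 × 0.078) / 0.2 = 18.8%. A reader can judge whether that is plausible.
3. Add a censoring-weighted run of the primary model, with weights from the last completed weekly survey: patient contact, PPE, prophylaxis, facility, and the HCW's own symptoms where these fall short of the case definition. Own symptoms are not among the SAP's model covariates.

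The cost is SAP text and additional analysis work on data already collected. No change to the survey or to follow-up is needed.

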8.7 Data Analysis

A separate statistical analysis plan (SAP) will be produced, providing detailed methods for the analyses outlined below.

Any deviations from the planned analyses will be described and justified in the final study report.

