8.7.4 Primary Analysis

A standard pharmaco-epidemiological inferential analysis will be conducted treating the registry data as a cohort with dynamic exposure to both prophylactic treatment and to COVID-19 infected patients and adjusting for potential confounding.

Both crude and adjusted hazards ratios will be estimated for prophylactic regimens of interest and any observed impact on the risk of infection among HCWs based on all statistical inferential models will be reported.

Outcomes will be adjudicated to exposure time based on prior decision rules agreed with the SAC. Hazards for each subject-week will be compared and adjusted for exposure to prophylaxis over time, exposure to COVID-19 positive patients over time and to other covariates, accounting for subject-level clusters. Repeated time-to-event analyses with competing risk will be carried out.

Handling of missing data and unexplained drop-outs will be discussed with the SAC. Interaction terms to be considered will also be discussed with the SAC and clinicians.

Matching or other balancing methods such as estimated propensity score matching, inverse probability weighting or marginal structural methods, or alternative methods, will be considered to potentially address the identified biases and allow for evaluation of association.

In case the number of infection cases is lower than anticipated to allow for such analyses, matched case-control analyses will also be considered.

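### SAP 6.7 makes the external-data analysis compulsory for an imprecise HR of 0.8 or less but leaves an equally imprecise HR of 1.25 to discretion

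*SAP*

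**What the plan says.** SAP section 6.7 closes with a conditional step. If the primary HR of treated versus control "is 0.8 or less, but no statistical significance can be established due to a small sample size, an alternative approach" is prescribed, and the sentence continues "such as empirical Bayesian meta-analysis will be employed to leverage published local data". No parallel step exists in the SAP for an HR above 1.

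Protocol section 8.7.6 has a related provision with different grounds and less force: "in the case of low number of events or unexpectedly low exposure to potential prophylactic treatments, alternative approaches will be considered", and information "from published local data could be leveraged using Bayesian modelling approach". Its example grounds are few events or low exposure, and neither refers to the direction of the result. The SAP states that it rests on protocol version 1.0, but the amendment list for version 1.1 names no change to 8.7.6, so the difference is not explained by versions.

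Three other statements bear on the point:

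- SAP section 6.1: "All statistical tests will be two-sided and at 5% level of significance".
- Protocol section 8.7: "Any deviations from the planned analyses will be described and justified in the final study report".
- Protocol section 8.7.4: "any observed impact on the risk of infection among HCWs based on all statistical inferential models will be reported".

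A shortfall is foreseen. SAP section 5 discusses what follows "If these sample sizes are not reached with respect the study population being exposed/non-exposed to potential prophylactic treatments", and says that significance may then not be reached. It attaches no direction to that.

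**The concern.** Whether supplementary evidence must be produced depends on which side of 1 the observed HR falls. An imprecise estimate suggesting benefit has to be followed by an analysis that borrows outside data. An equally imprecise estimate suggesting harm does not. The registry is meant to inform policy on prophylactic use, so an uncertain signal in either direction deserves the same treatment.

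The protocol's requirement to justify deviations does not restore the balance: leaving out an optional analysis at HR 1.25 is not a deviation.

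Three open terms add to the problem. The SAP does not define a small sample. It does not say how or when the published data are chosen. It does not say how the result is to be read beside the primary HR. Since the trigger is the observed HR, sources could be chosen after the estimate is known.

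**Working it through.** **Inputs from the documents.** N = 10,000, 20% unexposed, 10% risk in the unexposed, relative risk 0.78, 80% power (Protocol 8.7.7 and SAP 5); two-sided 5% (SAP 6.1); trigger HR 0.8 or less and not significant (SAP 6.7).

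**Assumptions.** The event counts of 100 to 600, the 25% widening of the standard error (SE) and the 5% exposed share below are illustrations, not document figures. The basic approximation is SE(log HR) = 1/√(events × exposed share × unexposed share), without frailty, facility or covariate terms.

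**1. The plan's own power.** Expected events are 2,000 × 0.10 + 8,000 × 0.078 = 824. Treating 0.78 as an HR, power = Φ(√(824 × 0.16) × |ln 0.78| − 1.96) = 81.4%, which agrees with the stated 80%. With no effect, events would be 10,000 × 0.10 = 1,000.

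**2. Equal evidence on both sides.** ln 0.8 = −0.2231 and ln 1.25 = +0.2231, so at equal SE the two p-values are identical.

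| Events (20/80) | SE | 95% CI, HR 0.8 | 95% CI, HR 1.25 | p, both |
|---|---|---|---|---|
| 100 | 0.250 | 0.49–1.31 | 0.77–2.04 | 0.37 |
| 200 | 0.177 | 0.57–1.13 | 0.88–1.77 | 0.21 |
| 400 | 0.125 | 0.63–1.02 | 0.98–1.60 | 0.074 |
| 824 | 0.087 | 0.67–0.95 | 1.05–1.48 | 0.010 |

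**3. When the rule can act.** An HR of 0.8 is non-significant only if SE exceeds ln(1.25)/1.96 = 0.1138. That is an information of 77.1, and 77.1/0.16 = about 482 events. At the planned 824 events (SE 0.087) the rule is inactive.

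**4. Chance of entering the step.** P(enter) = Φ((ln 0.8 − ln HR)/SE) − Φ((−1.96 × SE − ln HR)/SE). For example, at 200 events with true HR 1: Φ(−1.262) − 0.025 = 7.8%. The mirror event is a non-significant HR of 1.25 or more, for which the SAP has no rule.

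| Events | True HR 1: enter | True HR 1: mirror | True HR 0.78: enter | True HR 1.28: enter | True HR 1.28: mirror |
|---|---|---|---|---|---|
| 300 | 3.6% | 3.6% | 16.4% | 0.04% | 16.4% |
| 200 | 7.8% | 7.8% | 26.7% | 0.34% | 26.7% |
| 100 | 16.1% | 16.1% | 37.3% | 2.8% | 37.3% |

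Here 1.28 = 1/0.78. The chances of entering are maxima, because the undefined small-sample condition can only reduce them. They are chances of entering a step, not error rates.

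**5. Departures from the approximation.** If the full model widened the SE by 25%, the limit would be 482 × 1.5625 = about 753 events, and the no-effect chances at 300, 200 and 100 events would be 8.3%, 13.1% and 21.3%. At full size with 5% exposed and no effect, information is 1,000 × 0.05 × 0.95 = 47.5, SE 0.145, and the chance is 3.7%.

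**6. Why an event count would be a poor trigger.** At 600 events with the SE widened by 25%, nominal information is 96, above 77.1, so a count rule would call for no analysis. The actual SE is 0.128, and the present rule can still act (1.5% at HR 1, 8.4% at HR 0.78).

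**The case against.** The strongest defence is that the trigger reflects effect size as well as direction. It also leaves out favourable HRs between 0.8 and 1, and 0.8 lies close to the design relative risk of 0.78. It can be read as meaning that the planned effect was seen but the study was too small. The step does serve a real benefit, as the 26.7% at 200 events shows. But the documents do not give this rationale, and it would not explain why an equally imprecise harm of the same size has no rule.

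It can also be said that the step is less than strictly mandatory. Someone must judge whether the small sample is the reason for non-significance, and the method is only exemplified. That is true, but once the condition is judged met the SAP's wording is binding, whereas the protocol's is optional throughout.

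Other points stand and limit the concern. The step is a sensitivity analysis, the protocol allows external data in either direction, and the rule acts only if events fall at least about 40% short of plan or the SE is otherwise much wider than planned.

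Finally, a mirrored trigger (0.8 or less, or 1.25 or more) would be a smaller change. It would restore symmetry, but the analysis would still depend on the observed HR.

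**Conclusion.** The concern holds. Under two-sided testing, SAP 6.7 makes supplementary evidence compulsory only for a favourable estimate. It should be changed, but it does not threaten the primary analysis: that test and its 5% level are untouched, and the primary HR remains reported.

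The asymmetry matters if precision falls short, which is the situation the rule was written for. The SE limit of 0.1138 follows directly from the 0.8 cut-off and the 5% level. The event counts rest on the simple SE formula and the planned 20/80 split. The net effect on any combined estimate cannot be given, because it depends on published data that the SAP does not specify.

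**What to change.** Replace the HR-based trigger in SAP 6.7 with one based on precision, for example: *If the standard error of the log HR (treated versus control) from the primary model exceeds 0.1138, the external-data analysis will be performed whatever the value or significance of the HR.* With a Wald test this keeps every analysis that the present rule requires, since at or below that SE an HR of 0.8 or less is always significant. Because it uses the fitted model's SE, it also reflects the frailty, facility and covariate terms. Running the analysis in all cases is an acceptable alternative.

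In either case, fix the rule for selecting published sources and the model before the primary HR is seen, and report the result as supplementary, beside the primary HR.

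The cost is SAP wording and a pre-specified literature search. The analysis will be run more often, including when the HR is near or above 1 or already significant. At an assumed 200 events the SE trigger always acts. If the full model widened the planned SE by more than about 31% (0.1138/0.0871 = 1.31), it would act even at the full 824 events.

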7.1 Selection bias

- To minimize the impact of selection bias in the selection of participants, in each healthcare facility, the list of exposed HCWs will be obtained and all eligible HCWs will be offered enrollment. Furthermore, to assess the impact of selection bias, facility level data will be compared with HCW level data as outlined in section 5.3.1. Finally, an inverse probability weighting analysis (see section 5.4.2) will be undertaken. Incorporating data from relevant covariates will allow the reweighting of individuals to help achieve a more balanced analysis. This is achieved by increasing the weight of those individuals who were less likely to be enrolled in the study, and decreasing the weight of individuals who were more likely to be enrolled.

7.2 Survival bias

- To assess the impact of this bias, a metadata of healthcare facility level variables will be collected at time of the registry establishment and at the end of the study, including number of exposed to COVID-19 HCWs, number of HCWs who developed COVID-19 and who died from COVID-19 at each participating healthcare facility. This analysis is outlined in section 5.3.1.

